Safety and efficacy assessments will be conducted as per the Schedule of Assessments. Dosing will occur according to the selected regimen.

If the intramuscular (IM) dosing regimen is discontinued as a result of an independent data monitoring committee (IDMC) review from the ongoing Phase 3 studies, any subsequent analysis, or any other programmatic analysis, those participants who have not met any clinical management criteria for discontinuation will be discontinued permanently from the study and will enter into the LTFU Phase of the study.

LTFU Phase –Following the IM Regimen Only

Any participant who receives *at least one* dose of CAB LA and/or RPV LA and discontinues the CAB LA + RPV LA regimen for any reason must remain on suppressive HAART for at least 52 weeks after the last dose of CAB LA and/or RPV LA in order to prevent selective pressure on HIV during the period of declining drug exposures and the potential for selection of resistant mutants. **Investigators must discuss the choice of the follow-up HAART regimen with the Medical Monitor prior to initiating the new regimen with the participant. HAART therapy should be initiated within 4 weeks after the last monthly injection, however if withdrawn due to virologic failure, HAART should be initiated as soon as virologic failure is confirmed. Discuss with medical monitor.** The Long-Term Follow Up period (LTFU) will begin the day of the last CAB LA and/or RPV LA dose and continue for 52 weeks. These participants will not complete a Withdrawal visit, but will instead move directly into the LTFU as per the Schedule of Activities, Section 1.5. In addition, for participants who withdraw during the LTFU, the final visit will be considered the study withdrawal visit.

Participants will be assessed with clinic visits at months 3, 6, 9, and 12 during the LTFU Phase. Female participants of child bearing potential must continue to use adequate contraception methods for the entire year of follow up.

In order to assure that participants have access to HAART during the LTFU, ViiV Healthcare may supply HAART or reimbursement may be provided as needed during this phase. The LTFU Phase may be shortened or terminated at any time during the study for various reasons, e.g., better understanding of risks of development of resistance as CAB and RPV exposures decline, end of study timings, etc.

Staff study participants

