4.4. End of Study Definition

4.4.1. Study Completion

Patient Study Participants

The investigator is responsible for ensuring that consideration has been given to the post-study care of the patient study participant's medical condition.

Patient study participants are considered to have completed the study if they remain on therapy (i.e., have not permanently discontinued study intervention) and satisfy the following:

- Have completed all Month 12 evaluations
- remaining on study until commercial supplies of the CAB LA + RPV LA regimen becomes locally available, or initiates alternate antiretroviral therapy at the discretion of their HIV care provider, or
- development of CAB LA + RPV LA is terminated;

Upon completion of the above, patient study participants will exit the study and transition to commercial supplies of CAB LA + RPV LA, or alternate antiretroviral therapy at the discretion of their HIV HCP.

Until meeting the definition for study completion, participants will continue in the study until:

- the participant no longer derives clinical benefit,
- the participant meets a protocol-defined reason for discontinuation

Participants who withdraw from CAB LA + RPV LA and go into the LTFU Phase will be considered to have prematurely withdrawn from the study intervention.

Patient study participants will complete the 52-week Follow-Up phase required for participants who receive one or more injections with CAB LA or RPV LA. Assessments at the Follow-up visits should reflect any ongoing complaints (e.g., blood draws to follow a laboratory abnormality). Follow-Up visits are not required for successful completion of the study.

Study Staff Participants

Study Staff participants will have completed the study upon completion of all surveys and qualitative interviews after Month 12 evaluations have been completed at their site, per the Schedule of Activities (Section 1.5).

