- Participant requires substitution or dose reduction of CAB LA, RPV LA (oral bridging supply and potential for a second loading dose may be permissible following discussion with the Medical Monitor)
- Liver toxicity where stopping criteria are met and no compelling alternate cause is identified (see Section 10.6.2);

- Renal toxicity is met and no compelling alternate cause is identified;
- Corrected QT interval (QTc) >550 msec from three or more tracings separated by at least 5 minutes and considered causally related to IP. *Note: ECGs are not routinely conducted in this study.*
- Grade 4 clinical AE considered causally related to study drug;
- Participant has a Grade 3 or higher rash or Grade 2 rash with evidence of systemic involvement and no compelling alternative cause is identified.
- Participant withdrew consent

Safety data for all participants who receive any amount of study drug, including participants who withdraw from the study, will be included in evaluations of safety.

If a participant is prematurely or permanently withdrawn from the study, the procedures described in the Schedule of Activities Table, Section 1.5, for the in-clinic Withdrawal visit are to be performed. An in-clinic Follow-Up visit will be conducted 4 weeks after the last dose of study medication for participants with ongoing AEs, and serious adverse events (SAEs) related & not related to study drug and also any laboratory abnormalities that are considered to be AEs or potentially harmful to the participant, at the last on-study visit.

All data from the Withdrawal visit will be recorded, as they comprise an essential evaluation that should be done prior to discharging any participant from the study.

The following actions must be taken and documented in relation to a participant who fails to attend the clinic for a required study visit:

- a. The site must attempt to contact the participant and re-schedule the missed visit as soon as possible.
- b. The site must counsel the participant on the importance of maintaining the assigned visit schedule and ascertain whether or not the participant wishes to and/or should continue in the study.

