7.1.4. Managing Virologic Failure

Following study entry, no changes, or intensification of ART will be permitted prior to protocol-defined virologic failure, outside of the planned protocol regimens. Only plasma HIV-1 RNA values determined by the central laboratory will be used to assess virologic failure. Baseline plasma HIV-1 RNA is the assessment completed on study Day 1. The definition of confirmed virologic failure does not apply to participants in the LTFU Phase. These participants will be followed for the emergence of viral resistance.

Inadequate adherence or maladministration may be a cause for virologic failure and should be explored as a first step in the management of study participants (e.g., at the first indication of inadequate virologic response or rebound). Upon notification that a participant's HIV-1 RNA plasma level qualifies him/her as a suspected virologic failure (SVF), the Investigator should query the participant regarding intercurrent illness, recent immunization, or interruption of oral therapy.

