7.1.4.3. Confirmed Virologic Failure

Participants with CVF must be discontinued from study treatment. However, participants who have received at least one dose of CAB LA or RPV LA prior to confirming virologic failure will remain in the study on oral HAART in the LTFU Phase.

A plasma sample from the suspected virologic failure visit as well as Day 1 (if baseline HIV-1 RNA level ≥ 200 c/mL) will be sent for genotypic and phenotypic resistance testing and the result made known to the Investigator when available. A plasma sample from the confirmation visit will be obtained for storage. This sample may be used for possible future analyses, e.g., for genotypic and phenotypic analyses of participants who experience virologic failure.

For all participants who meet CVF, baseline and suspected virologic failure plasma samples with HIV-1 RNA level ≥ 200 c/mL will be analyzed in an attempt to obtain genotype/phenotype data on as many samples as possible. Plasma samples for storage will also be obtained at unscheduled visits including confirmation of CVF. Participants may continue to receive study drug at the discretion of the investigator until results of resistance testing are available at which time the participant must be discontinued from the study. Even if genotype/phenotype data cannot be generated, participant must also be discontinued from the study intervention.

If a participant is prematurely discontinued from the study intervention, the investigator must make every effort to perform the Withdrawal Visit evaluations outlined in the Schedule of Activities Table, Section 1.5. These data will be recorded as they comprise essential evaluations needed to be done before discharging any participant from the study.

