10.6.4. Grade 3 Toxicity/Adverse Event

Participants who develop a Grade 3 AE or toxicity should be managed as follows:

- If the Investigator has compelling evidence that the Grade 3 AE or toxicity has not been caused by IP, dosing may continue after discussion with the Medical Monitor.
- Participants who develop a Grade 3 AE or toxicity, which the Investigator considers related or possibly related to the IP, should have the IP withheld and be rechecked each week until the AE returns to Grade 2. Once the AE is Grade ≤ 2 , IP may be re-started.
- Should the same Grade 3 AE recur within 28 days in the same participant, the IP should be permanently discontinued and the participant withdrawn from study.

- Participants experiencing Grade 3 AEs requiring permanent discontinuation of IP should be followed weekly until resolution of the AE and to have withdrawal study evaluations completed. A follow-up visit should be performed 4 weeks after the last dose of IP. Any participant receiving at least one dose of CAB LA and /or RPV LA who discontinue IP / Withdraw will initiate treatment with HAART and enter the Long-Term Follow-Up Phase for 52 weeks of follow up.
- Participants with Grade 3 asymptomatic laboratory abnormalities should be investigated for all potential non-drug related causes, and, following discussion with the Medical Monitor, may continue IP if the Investigator has compelling evidence that the toxicity is not related to IP, with the exception of liver chemistry stopping criteria (See Section 10.6.2). Isolated Grade 3 lipid abnormalities do not require withdrawal of IP.

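### Injected participants who stop treatment and enter long-term follow-up are told both to skip and to complete the Withdrawal evaluations, so HIV-1 RNA and safety data at discontinuation may go uncollected

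*Protocol*

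**What the plan says.** **Skip.** Section 1.3 (LTFU Phase) covers any participant who has had at least one dose of CAB LA and/or RPV LA and discontinues the regimen for any reason: "These participants will not complete a Withdrawal visit, but will instead move directly into the LTFU as per the Schedule of Activities".

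**Complete.** Section 7.1.4.3 says of a participant prematurely discontinued from study intervention that "the investigator must make every effort to perform the Withdrawal Visit evaluations". This follows text in the same section that sends injected participants with CVF to LTFU. Section 4.4.1 says that those who come off the regimen and "go into the LTFU Phase will be considered to have prematurely withdrawn from the study intervention", so LTFU entrants meet the trigger in 7.1.4.3.

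**Both in one bullet.** Section 10.6.4 says participants permanently stopping for a Grade 3 event "should be followed weekly until resolution of the AE and to have withdrawal study evaluations completed", and the same bullet sends anyone injected to LTFU. Section 10.6.5 does the same for Grade 4 events, in softer terms (participants are encouraged to complete the evaluations).

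**Less clear.** Section 7 says that the scheduled procedures "for the in-clinic Withdrawal visit are to be performed", but its trigger is withdrawal from the study rather than from treatment.

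**Start of LTFU and CVF.** Section 1.3 says: "The Long-Term Follow Up period (LTFU) will begin the day of the last CAB LA and/or RPV LA dose". Section 7.1.4 says: "The definition of confirmed virologic failure does not apply to participants in the LTFU Phase".

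**The concern.** The Withdrawal (WD) column of Table 3 is the only scheduled collection tied to stopping treatment. It holds HIV-1 RNA, stored plasma, CD4+, chemistry/haematology, ECG, injection-site assessment, vital signs and weight. Several of these feed stated secondary endpoints: HIV-1 RNA below 50 c/mL over time, CVF, injection-site reactions, and laboratory values and abnormalities over time.

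If a site follows Section 1.3, the next scheduled sample is at LTFU Month 3. If it follows Section 7.1.4.3, there is a sample when treatment stops. Data from discontinuing participants would then depend on which section a site read, and these participants are the most informative for failure and tolerability. There is a second gap. LTFU starts on the day of the last injection and CVF does not apply in LTFU, so the protocol does not say whether a sample taken at the decision to stop counts as on-treatment.

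**Working it through.** The protocol states no figure for this point, so there is none to reproduce. The check has three parts.

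**1. Do the two rules reach the same people?**
- Section 1.3 applies to those with at least one long-acting dose who discontinue for any reason and move into LTFU.
- Section 7.1.4.3 applies to those prematurely discontinued from study intervention.
- Section 4.4.1 puts LTFU entrants in the second group, so Section 7.1.4.3 cannot be confined to people who stop during the oral lead-in.
- Both patient analysis sets in Section 9.3 require at least one dose of CAB LA + RPV LA, so every analysed participant who moves into LTFU falls under both rules.

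**2. Sampling gap if the Withdrawal evaluations are skipped.** Inputs:
- Table 3: HIV-1 RNA at Months 1, 2, 4, 6, 8, 10, 12; chemistry/haematology at Months 1, 2, 4, 6, 9, 12.
- Section 1.3 and Table 5: first LTFU visit 3 months after the last dose.

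For a last injection at Month m (1 to 11), gap = (m + 3) − (last scheduled sample at or before m).

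| Last injection (Month) | HIV-1 RNA gap (months) | Chemistry/haematology gap (months) |
|---|---|---|
| 1, 2, 4, 6 | 3 | 3 |
| 3, 5, 7 | 4 | 4 |
| 8 | 11 − 8 = 3 | 11 − 6 = 5 |
| 9 | 12 − 8 = 4 | 12 − 9 = 3 |
| 10 | 13 − 10 = 3 | 13 − 9 = 4 |
| 11 | 14 − 10 = 4 | 14 − 9 = 5 |

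The range is 3 to 4 months for HIV-1 RNA and 3 to 5 months for chemistry/haematology. Section 1.3 has HAART starting within 4 weeks of the last injection, so an LTFU Month 3 value does not replace an end-of-treatment value. Table 5 does not schedule ECG, injection-site assessment, vital signs or weight at all. These are gaps between scheduled samples; any unscheduled draw shortens them.

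**3. Reach into CVF.** Section 7.1.3 needs two consecutive HIV-1 RNA values of at least 200 c/mL, and Section 7.1.4.2 asks for a repeat test on suspected failure whether or not there is a Withdrawal visit. A participant stopped because of CVF is already counted. Two situations remain:
- a suspected failure not repeated before the participant leaves injections;
- a rebound first detectable at stopping.

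The protocol gives no count for either. Taking 0 to 2 missed cases as an assumption and the planned maximum of 135 as denominator, each case moves the proportion by 1/135 = 0.74 points. Exact (Clopper-Pearson) 95% intervals:

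| CVF cases | Proportion | 95% CI |
|---|---|---|
| 0/135 | 0% | 0 to 2.7% |
| 1/135 | 0.74% | 0.02 to 4.1% |
| 2/135 | 1.48% | 0.18 to 5.3% |

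**The case against.** There is a good case for a narrower reading, and much of it stands.

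- **Section 7 need not conflict.** It speaks of withdrawal from the study, and its opening paragraph says people who stop treatment and enter follow-up are not withdrawn from the study. It can be read alongside Section 1.3. Footnote o on the WD column of Table 3 likewise describes a visit for those not entering LTFU. This stands, so Section 7 needs clarifying but does not carry the point.
- **Not every discontinuing participant is affected.** Those who leave the study outright (consent withdrawn, lost to follow-up) do not move into LTFU, and Sections 7 and 7.2 govern them without contradiction. This stands.
- **Section 7.1.4.3 gives as its reason evaluations needed before a participant is discharged from the study**, and LTFU entrants are not discharged. This weakens the conflict but does not remove it: the trigger in that sentence is stopping the intervention, the section has just sent injected participants to LTFU, and Sections 10.6.4 and 10.6.5 ask for both.

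A reader might infer that HIV-1 RNA and safety laboratory data are lost for these participants. The documents do not support that. The last scheduled HIV-1 RNA is at most one month before the last dose, and HIV-1 RNA, CD4+ and chemistry/haematology resume at LTFU Month 3. Participants permanently stopping for Grade 3 or 4 events are also followed weekly until resolution.

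A reader might also infer that CVF will be undercounted. That is not shown either, because the repeat test in Section 7.1.4.2 is independent of the Withdrawal visit.

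**Conclusion.** The contradiction is real and unresolved. It rests on Section 1.3 against Section 7.1.4.3 read with Section 4.4.1, supported by Sections 10.6.4 and 10.6.5. It applies to injected participants who stop and enter LTFU. What is at risk is the evaluation at discontinuation, not the participant's whole record. Undercounting of CVF is a narrow possibility, worth 0.74 points per missed case on a denominator of 135; that is small in absolute terms, but noticeable if the observed count is near zero.

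The protocol gives no discontinuation rate. If 10 to 15% discontinued (an assumption), 135 × 0.10 = 13.5 to 135 × 0.15 = 20.25, or about 14 to 20 people, could lack an evaluation at discontinuation, provided all entered LTFU and all their sites followed Section 1.3. The figure does not mean that many people are without HIV-1 RNA or laboratory data.

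The endpoints concerned are secondary and descriptive, and no hypothesis test is planned. The point should still be corrected, because collection would otherwise differ between sites and the remedy is cheap.

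**What to change.** 1. Reconcile Sections 1.3, 7.1.4.3, 10.6.4 and 10.6.5 with the WD columns of Tables 3 and 5 so that, for endpoint data, the existing WD-column HIV-1 RNA, stored plasma and safety evaluations are collected at discontinuation from LTFU entrants too.
2. Clarify in Section 7, and in footnote o of Table 3, whether the Withdrawal visit is meant for those leaving the study, those stopping treatment, or both.
3. Reconcile the start of LTFU in Section 1.3 with the CVF exclusion in Section 7.1.4 by stating whether a sample taken at discontinuation is analysed as on-treatment for the HIV-1 RNA and CVF endpoints. This is an analysis statement. The CVF definition in Section 7.1.3 is set for clinical management, and this point proposes no change to how participants are managed.

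The cost is one already specified set of evaluations for each participant who discontinues into LTFU, plus consistent wording across several sections rather than the edit of a single sentence.

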7.2. Participant Discontinuation/Withdrawal from the Study

- A participant may withdraw from the study at any time at his/her own request, or may be withdrawn at any time at the discretion of the investigator for safety,

behavioral, compliance or administrative reasons. This is expected to be uncommon.

- At the time of discontinuing from the study, if possible, an early discontinuation visit should be conducted, as shown in the Schedule of Activities, Section 1.5. See SoA, Section 1.5 for data to be collected at the time of study discontinuation and follow-up and for any further evaluations that need to be completed.
- The participant will be permanently discontinued both from the study intervention and from the study at that time.
- If the participant withdraws consent for disclosure of future information, the sponsor may retain and continue to use any data collected before such a withdrawal of consent.
- If a participant withdraws from the study, he/she may request destruction of any samples taken and not tested, and the investigator must document this in the site study records.

7.3. Lost to Follow Up

A participant will be considered lost to follow-up if he or she repeatedly fails to return for scheduled visits and is unable to be contacted by the study site.

The following actions must be taken if a participant fails to return to the clinic for a required study visit:

- The site must attempt to contact the participant and reschedule the missed visit as soon as possible and counsel the participant on the importance of maintaining the assigned visit schedule and ascertain whether or not the participant wishes to and/or should continue in the study.
- Before a participant is deemed lost to follow up, the investigator or designee must make every effort to regain contact with the participant (where possible, 3 telephone calls and, if necessary, a certified letter to the participant's last known mailing address or local equivalent methods). These contact attempts should be documented in the participant's medical record.
- Should the participant continue to be unreachable, he/she will be considered to have withdrawn from the study.

Discontinuation of specific sites or of the study as a whole are handled as part of Section 10.1.

8. STUDY ASSESSMENTS AND PROCEDURES

Protocol waivers or exemptions are not allowed with the exception of urgent actions to address immediate safety concerns. Therefore, adherence to the study design requirements, including those specified in the Schedule of Activities Table, Section 1.5, are essential and required for study conduct.

This section lists the procedures and parameters of each planned study assessment. The exact timing of each assessment is listed in the Schedule of Activities, Section 1.5.

The following points must be noted:

If assessments are scheduled for the same nominal time, THEN the assessments should occur in the following order:

1. 12-lead ECG
2. vital signs
3. blood draws

•The IRB/independent ethics committee (IEC) will be informed of any safety issues that require alteration of the safety monitoring scheme or amendment of the Informed Consent Form.

Please refer to Section 10.12, Appendix 12 in for study management information during the COVID-19 pandemic.

8.1. Screening Assessments

Eligibility criteria must be carefully assessed at the Screening visit. Physical examinations should be conducted as part of normal routine clinical care. Background information to be collected at Screening includes demography and prior ART history.

Eligible participants may be enrolled immediately as soon as all Screening assessments are complete and the results are available and documented. All participants will complete the screening period of approximately 21 days prior to Baseline (Day 1) during which all clinical and laboratory assessments of eligibility must be performed and reviewed. All Screening results **must** be available prior to enrollment.

All information about the participant's current regimen must be available for review by the Principal Investigator or designee prior to enrollment. Source documents from other medical facilities must be located/received during the 21 day screening period and under no circumstances may the participant be randomized in the absence of source documentation even if there are delays in receipt of this information.

Participants who meet all entry criteria and are enrolled will be assigned a randomization number. A single repeat of a procedure/lab parameter is allowed to determine eligibility (unless otherwise specified). Participants not meeting all inclusion and exclusion criteria at initial screen may be rescreened one time within 4 weeks and receive a new participant number. Participants who are enrolled into the trial and subsequently withdrawn from the study for any reason may not be rescreened.

